3.0 STUDY DESIGN

3.1. CTC training and piloting. Intervention staff from LA and SF will participate in a week-long CTC training led by Co-I [name] and consultant [name]. The goal of the training is to develop the knowledge and skills necessary to faithfully and effectively deliver the CTC intervention. Training modules include information about active listening, safer injection practices, overdose prevention, and risk associated with injection initiation. The peer handbook training manual is provided in *Appendix A*. Training will be completed by the four interventionists (2 from each site), study coordinator/directors at each site, and the MPIs. Following training, each interventionist will pilot the CTC intervention with four PWID at each site (2 interventionists per site, 4 PWID per interventionist, 16 PWID total). The CTC information Guide (*Appendix B*) was developed by Drs. [name] and [name]. Participants will be recruited for community settings and undergo informed consent prior to undergoing the intervention session (see **Appendix C for informed consent form**). Each practice session will be audio-recorded and reviewed by the MPIs and project directors for fidelity to intervention protocols. A brief semi-structured exit interview will be conducted with the PWID participants to solicit their input on feasibility, acceptability, and satisfaction with the intervention session (**Appendix D**). PWID will receive \$30 for completing the pilot CTC session and exit interview. Modifications to terminology used in the intervention and other minor changes will be considered based on this feedback. Following completion of training and piloting, a cross-site meeting with staff from each site and Drs. [name] and [name] will be held to finalize any changes to the CTC curriculum.

Interventionists will also devote a week to learning and practicing the equal attention control intervention (see **Section 7.0**). To prevent interventionist contamination, one interventionist from each site will conduct the CTC intervention for the first half of data accrual while the other interventionist will implement the equal attention control. Interventionists will then switch for the second half of data collection.

We will also conduct up to 20 pilot interviews (10 in each site) of the baseline questionnaire (Appendix H). Pilot interview participants will be self-identified persons who inject drugs and are 18 years of age or older. The pilot interview will occur in a private one-on-one session with a trained research interviewer. Participants will receive \$15 USD for completing the interview. Information from these interviews will be used to revise specific questionnaire items for comprehension and clarity.

3.2. Sampling. We will use targeted sampling methods developed by Watters and Biernacki to recruit PWID into the screening component of this study (N~1,200).⁷⁵⁻⁷⁸ This method is a systematic approach to sampling

hidden and uncounted populations when true random sampling is not feasible and has been widely used in epidemiological

studies of drug users including our own.⁵⁸⁻⁶⁰ We chose targeted sampling for four reasons: (1) in San Francisco, targeted sampling has been found to reach a more diverse population of PWID than RDS;⁷⁹ (2) several unresolved methodological issues regarding the analysis of RDS data could potentially obfuscate findings;⁸⁰⁻⁸² (3) in cohort studies, RDS referral chains can get easily broken through loss to follow-up, thus requiring a large amount of data imputation; and (4) it is not possible to analyze data across two cities because the referral chains cannot extend between cities.

3.3. Field sites and interview setting. Data collection will occur at community-based field sites conveniently located for PWID to access and conducive to private confidential interviews and intervention sessions. In the past, we have rented space in community-based agencies and single-room occupancy hotels.

3.4. Recruitment and screening for eligibility. Subjects will be recruited into the study by community outreach workers with extensive experience working in LA and SF PWID communities. The outreach workers will walk through specified recruitment areas delineated in the targeted sampling plan, engage potential study participants in conversation, and distribute socks, water, other supplies and referral information when necessary. The outreach workers will briefly describe the study procedures to potentially eligible subjects. Individuals interested in participating will be given a card with the hours and location of the local community field site. Upon arrival at the community field site, potential study participants will be taken to a private space to meet briefly with the Study Coordinator, who will ask a series of questions evaluating age and ability to provide informed consent to determine eligibility for the study. Eligible study participants will be given a same-day appointment, either immediately or very shortly thereafter for the screening interview. *Figure 1* describes the participant flow through the study.

Recruitment for the elucidation sub-study will be from the parent study. Participants returning for follow-up interview or check-ins will be told about the sub-studies and offered an opportunity to participant in one or both of the sub-studies. Eligibility for the parent study will be the same for the sub-studies. However, we will not rescreen potential participants for recent drug use.

3.5. Eligibility and inclusion/exclusion criteria: To be eligible to participate in the study potential subjects must report: (1) Recent injection of illicit drugs (past 30 days) as verified by checking for signs of venipuncture ("tracks");⁸⁴ (2) age 18 years or older; (3) ability to speak English, and (4) ability to provide informed consent. Exclusion criteria less than 18 years of age, no physical evidence of recent injection drug use, insufficient English language comprehension, and intoxication. Intoxicated potential participants will be invited to return for eligibility screening once they are sober. Eligibility screening will be conducted by Project Coordinators.

3.6. Biometrics data collection to prevent duplicate participation. To prevent duplicate participation, all screening-eligible participants will provide the following biometric information: race/ethnicity, age, eye color, height, circumference of wrist and length of forearms, and the location of notable scars and tattoos (Appendix F). Use of these measures has been found to be acceptable to PWID and provide sufficient information to deter, detect, and prevent duplicate enrollment of participants.⁸⁵ These same procedures were successfully implemented in the pilot study conducted by [name].⁷

No biometric data will be collected as part of the elucidation study.

3.7. Informed consent. Informed consent will be obtained in a confidential space prior to the baseline interview (**Appendix E**). The Study Coordinator or research interviewer will read the consent form aloud individually to each participant. Questions and concerns will be addressed throughout the consent process. All study procedures will be approved by the Institutional Review Boards at the University of Southern California. Elucidation information consent forms are provided in Appendix L (HAV/HCV) and M (Drug effects and withdrawal).

3.8. Locator form. For retention purposes, participants will be asked to provide contact information (phone number, e-mail address, day-time hangouts), the names and phone numbers of up to three contact persons, and the names and locations of social service agencies they utilize (**Appendix B**). Participants will be requested to sign releases authorizing the staff to contact these agencies to locate them if they miss an appointment (see **Appendix J**). They can refuse to provide this information and still participate in the study. We have regularly asked and obtained this information in studies with PWID in LA and SF. No identifying information will be collected from elucidation sub-study participants.

3.9. Baseline interviewing. Baseline interviews will be conducted in English using computer assisted personal interview. The interview will occur in an one-on-one session with a trained research interviewer. Participants will receive \$15 for completing the screening interview. We will conduct approximately 48 baseline interviews per month (24 interviews at each site per month) until 538 participants have completed the CTC intervention and 538 participants have completed the equal attention control intervention (*Timeline, Table 1* see below).

The elucidation study interviews will be offered to current study participants. Study 1 (HAV/HCV) is a quantitative survey that covers topics related to HAV risk (sanitation issues) and HCV treatment (Appendix N). Study 2 is qualitative in nature and addresses effects and withdrawal symptoms (Appendix O). Procedures in section 3.10 to 4.0 do not apply to the elucidation study.

3.10. Randomization. Following completion of the interview each participant will be randomly assigned (using urn,⁸⁹ see **Section 6.0**) to receive either the CTC intervention or the equal attention control nutrition intervention session, according to a computer-generated random numbers program. 3.11. Intervention fidelity and quality control. All intervention trainings will be audio-recorded. To ensure intervention fidelity, the Study Coordinator will listen to all recorded trainings for the first month and then a 10% random sample thereafter. The Study Coordinator will score intervention fidelity on a standardized form that will include a list of all intervention manual components. Interventionists will receive reports from these sessions. If interventionists score less than 95% fidelity on any session, they will be retrained by the Study Coordinator and tape recordings of their next sessions will be reviewed until a 95% fidelity rate is obtained. Given our past experience, training plan and oversight, we expect fidelity to rarely fall below 95%. Participants will also complete a short questionnaire on their satisfaction with the intervention session to which they were exposed (see **Appendix K**).

3.12. Cohort maintenance and recapture strategies. We will use multiple proven strategies to retain cohort members at the 6-month and 12-month follow-up interviews. First, during enrollment for the proposed study, we will collect detailed tracking information, as described in **Section 3.8**. The Study Coordinator will enter tracking information into a Microsoft Access database on a password-protected laptop computer. We will use this information to locate participants who miss appointments. Second, participants will have a monthly check-in appointment with study staff, which will be held at field sites in the recruitment communities, and will receive a \$10 incentive for attending. At check-in, tracking information will be verified and updated. [name] has conducted two NIDA-funded cohort studies that compared the effectiveness of incentivized check-in appointments with that of standard tracking by outreach workers^{67,90} and found that paying each cohort member \$10 monthly yields much higher return rates and is less costly than relying on staff outreach alone. Third, we will use graduated incentives for the interviews: \$15 for the screener/baseline and \$20 for each of the 6-month and 12-month follow-up interviews. We will also allow the participants to return for up to one month past their study appointments. Study participants will continue to be eligible for the study throughout the follow-

up period even if they miss their check-in appointments. To minimize any potential participation biases during check-ins, research staff will only update contact information and not discuss any substantive topics.

3.13. Follow-up interviews at 6 and 12 months. Similar to baseline/screening interviews, 6- and 12- month follow-up interviews will be conducted using CAPI in a one-on-one session with a trained research interviewer. Participants will be remunerated \$20 for each follow-up interview they complete.

3.14. Timeline: As described in **Table 1**, below, following training and piloting, baseline data collection will commence in May 2016 and continue until December 2018.

Table 1. Project Timeline

	Year 01			Year 02			Year 03				Year 04					
Activity	Q3	Q4	Q1	Q2	Q3	Q4	Q1	Q2	Q3	Q4	Q1	Q2	Q3	Q4	Q1	Q2
Calendar year	'15	'15	'16	'16	'16	'16	'17	'17	'17	'17	'18	'18	'18	'18	'19	'19
RCT Baseline				Х	Х	Х	Х	Х	Х	Х						
6-month follow-up						Х	Х	Х	Х	Х	Х	Х				
12-month follow-up								Х	Х	Х	Х	Х	X	Х		

3.15. Data collection measures. Data collection measures were selected based on their relevance to evaluating CTC, applicability to social learning theory and IMB model, and potential as confounders. Items from each area are described below and a draft of the baseline questionnaire is included in **Appendix H**.

3.16. Main outcome measures for **Aims 1 & 3** will be the number of people initiated in the past 6 months. This item will be assessed by asking the following questions: "In the past 6 months, have you helped someone get their first hit (the first time they ever injected)?" If participants respond Yes, they will be asked the following question: "How many people (total) have you helped get their first hit (inject for the first time) in the past 6 months?" Not applicable responses (or No on the first item) will be recoded as zeros for data analysis purposes. For **Aims 2 & 3** we will ask the following items: "In the past 6 months, have you been asked to help someone inject an illicit drug for the first time?" Participants responding 'yes', were then asked how many people had asked them to provide their first injection. The time frame of 6 months allows us to assess changes in the outcome at 6 months (as was done in the pilot) and 12 months. The use of a count approach for outcome variables enables us to account for changes even if they only occur among high volume initiators and those with multiple injection initiation social learning risk. We will also collect data on sex risk, specifically, unprotected sex, multiple sex partners, and sex risk by partner type^{91,92} for purposes of determining the efficacy of the attention control condition although this is not an aim of the proposed study.

3.17. Main independent measures will be intervention condition: CTC or equal attention control group for Aims 1 & 2. For Aim 3, we will also evaluate three injection initiation social learning risks as mediating variables. These items are intended to capture social learning constructs (i.e., observation of behavior, supportive interactions, and reinforcement) within the social processes of injection initiation. To capture observing, we will ask current PWID the following item: "In the past 6 months, have you injected drugs in front of someone who has never injected an illicit drug?" To capture interaction, we will ask "In the past 6 months have you explained or described how to inject to someone who has never injected an illicit drug (i.e., a noninjector)?" To measure reinforcement we will ask, "In the past 6 months, have you spoken positively about injecting with someone who has never injected an illicit drug?" Each item is a binary variable (Yes/No) where Yes denotes endorsing the injection initiation social learning risk assessed.

We will also collect IMB constructs related to injection initiation and sex risk. For the information construct, we will collect true or false knowledge items on sex-related HIV prevention provided by Kalichman, Simbayi and others^{5,6} and develop similar items for injection initiation risks. To develop injection initiation risk motivation and behavioral skill items we will follow procedures outlined by Kalichman, Simbayi and others.^{5,6} For sex-risk related motivation and behavioral skill items we will draw from existing studies.^{5,6} All injection initiation risk and sex-related IMB skill items will all be pilot tested. Psychometric properties of existing measures are known and acceptable, however, we will test both existing and new measures for their applicability to this study population. Drafts of all items are provided in the baseline survey (**Appendix H**).

3.18. Potential confounding variables or covariates will be selected from the following domains: sociodemographics/economics, current drug use patterns, blood borne infectious disease risks, experimental condition contamination, and social desirable responding. Socio-demographic and socioeconomic characteristics will be collected from each participant, including race/ethnicity (with options for multiple racial/ethnic identification), age, education, income/income sources, living arrangements (including homelessness), and relationship status. Drug use history and current use patterns have previously been shown to be associated with initiation of injection-naive people.⁵⁹ In the proposed study, we will assess frequency of injection and non-injection in the past 30 days for the following drugs: crack cocaine, cocaine, heroin, methamphetamines, speedball (admixture of heroin/cocaine), goofball (admixture of heroin/methamphetamines), prescription drug misuse (e.g., opiates, tranquilizers, stimulants, sedatives, methadone, and buprenorphine), and marijuana. The drug use items have been found to be valid and reliable.^{16,17} *Injection-related HIV and HBV/HCV risk* will be captured using modified items from NIDA's cooperative agreement study of the 1990s (the "RBA").⁹⁶ These items have been found to be valid and reliable.^{15,17} *Socially desirable response set measure* (SDRS-5) contains five items adapted from the Marlowe-Crowne Form A measure of social desirability. Respondents rank each item on a 4-point scale ranging from 1 (strongly disagree) to 4 (strongly agree).⁹⁷

3.19. Six-month and 12-month follow-up measures will include all main outcome (**Section 3.16**.) and independent variables (**Section 3.17**) as well as socio-demographic and economic variables that could change during the 6-month follow-up periods (e.g., relationship status, homelessness, income). We will also assess contamination at 6-month follow-up interview. It is possible that skills learned by the CTC participants may be shared with participants in the equal attention control group. This type of contamination cannot be prevented, but it can be measured. At 6-month interview, participants in both conditions will be asked if they have had conversations with other PWID on a variety of health issues, including injection initiation, initiation injection social learning risk, sex risk, and other items to mask the intent of the question. We will also ask them about intervention phrases such as "Change the Cycle" to assess whether control group participants are familiar with them. A similar approach has been used in other intervention studies among PWID to identify exposure to an intervention.⁹⁸ We will ask questions about satisfaction with and usefulness of the CTC intervention or the equal attention control 12 month survey. The domain lists for items to be included in the 6 and 12 month survey are provided in **Appendix I**.

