6.0 STRATIFICATION/DESCRIPTIVE FACTORS/RANDOMIZATION SCHEME

- 6.1 Stratification factors. Not applicable.
- 6.2 Descriptive factors. Based on prior studies with PWID, we anticipate the following characteristics: The majority will be over the age of 50, roughly a third will be white, a third will be African American, and 25% will be Latino. About 25% will be female. The vast majority will be heroin injectors although a third will also report methamphetamine use, and 10% will report cocaine and opiate prescription injection in the last 30 days.
- 6.3 For participants in the RCT, randomization will be accomplished using urn. Urn randomization is an adaptive biased-coin randomization method.⁸⁹ In brief, it means you not only replace the ball that is chosen out of a hat (for example: blue for experimental and red for control condition), but you add a ball from the opposite color as well. The urn design forces balance for studies

with a large number of confounders as it approaches complete randomization and full balance as the size of the trial increases. Consequently, the urn design is not as vulnerable to experimental bias as are other restricted randomization procedures.

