change/reduction in the number of initiations over the 3 observation times (1 to i). The first part of the analysis will involve characterization of the measurement model for the change over time from T0 to T1 and from T1 to T2. As shown in Figure 3, the model will include a treatment covariate representing the effect of the CTC intervention on changes over time for the binary (sU) and count (sZ) latent variables, and it may contain other covariates identified as having been distributed differentially by condition at baseline or associated with loss to follow-up. Note that if there are no differences at baseline in preliminary bivariate analyses, there is no need to include a treatment effect on the intercept for the SEM because with no differences at baseline, the intercept test for difference is likely to be non-significant so there is no value in risking the extra degrees of freedom. Through model constraints, we will also examine specific differences between conditions within time points (e.g., T1 or T2) and between time points (e.g., change over time from T0 to

Figure 3. Two-Part Zero-Inflated Poisson SEM

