T1). There will be little need for additional covariates to control for potential inflation of the correlations due to recruitment sites, as the targeted sampling will ensure full coverage across the locations where PWID congregate in LA and SF. We will, however, explore differences between the two sites, and may introduce a control variable to account for large-scale environmental differences between the two sites. To avoid any analytic decisions being driven by a desire for a certain result, the statistician and data analysis team will be blinded as to whether 0 or 1 denotes the treatment or control condition until the analyses are completed. There is also potential for contamination, which we will assess by asking the respondents in the control condition their level of exposure to intervention components, as described in Section 3.5.17.3. We will follow procedures outlined by Keogh-Brown et al. (2007) using complier average causal models (CACE),¹⁰⁴ in which the bias associated with contamination is significantly reduced by averaging the estimated causal effect over classes of participants that differ in the level of exposure to contamination. Each person in the control group will be assigned to a class, depending on their level of exposure and type of exposure, using latent classification techniques utilized by [name] in previous publications.¹⁰⁵ Lastly, we will compare differences in examining the rate of change versus the standardized difference at each follow-up point (e.g., compare counts of injection initiation at 6m and 12m) and test for differences by condition. The latent change model has more power than the raw difference approach, and we will present differences in our published work if the outcome is sensitive to model estimation.

Aim 2: To test the efficacy of CTC on reducing the number of times PWID are asked to initiate (counts) someone into injection. H2: PWID who receive CTC will report having been asked fewer times to initiate someone into drug injection at 6 and 12 months as compared with PWID in the equal attention control condition. This model will be estimated in the same manner as the model for the outcome of the actual number of reported counts, save that this one will estimated using the self-reported counts by the respondent regarding being asked to initiate another person.

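### Arm and interventionist coincide within each city and accrual half; the models adjust for neither interventionist nor half, so staff differences cancel only if the undefined halves are about equal in size

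*Combined protocol and SAP*

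**What the plan says.** Section 3.1: "Training will be completed by the four interventionists (2 from each site", so each city has two people delivering sessions. To limit contamination, "one interventionist from each site will conduct the CTC intervention for the first half of data accrual" and the other gives the control session. "Interventionists will then switch for the second half of data collection". Neither half is defined by count or by date.

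Timing is given in three places. Section 3.14 says "baseline data collection will commence in May 2016 and continue until December 2018". Table 1 in the same section marks baseline only from Q2 2016 to Q4 2017. Section 3.9 says "We will conduct approximately 48 baseline interviews per month".

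On allocation, Section 6 states "6.1 Stratification factors. Not applicable".

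On analysis, the Aim 1 model in Section 13.1 has a treatment covariate, and "it may contain other covariates identified as having been distributed differentially by condition at baseline or associated with loss to follow-up". For the two cities the team "may introduce a control variable to account for large-scale environmental differences between the two sites". Fidelity may enter as a covariate. Aim 2 is modelled in the same way. Section 13 names no interventionist term, no accrual-half term and no effect by half. Section 13.2 assumes an intracluster correlation of 0.5 without naming the cluster.

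**The concern.** Inside any one city and half, every CTC participant saw one person and every control participant saw another. A difference between those two people, for example in rapport or in how it affects later attendance, cannot be separated there from a difference between CTC and control. The switch is the only feature of the design that separates them, and it works by averaging one half against the other. If more participants are enrolled before the switch than after it, the averaging is incomplete and part of the staff difference stays in the CTC estimate. The model as written would not remove it. The covariate rule is optional and depends on the data, and it was written for baseline and attrition variables, so it does not secure the adjustment.

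**Working it through.** **Plan's own figures.** Section 13.2 recruits 1,076 (538 per arm) and expects about 800 at 12 months after 25% attrition. 1,076 x 0.75 = 807, and 800 / 0.75 = 1,067, so this is consistent. With 2 cities x 2 halves x 2 arms, each cell holds about 1,076 / 8 = 134.5 people enrolled, or 800 / 8 = 100 analysed.

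**Structure.** Within a city, code arm A, half H and interventionist I as -1 or +1. Then I = A x H exactly. With equal halves A is uncorrelated with I and with H, so a constant staff difference adds nothing to the arm contrast. This is exact on an additive scale and approximate in a zero-inflated Poisson model. If a share f is enrolled before the switch, the unadjusted contrast keeps (2f - 1) of the staff difference: 0 at f = 0.50, 0.20 at 0.60 and 0.43 at 0.714.

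**How unequal could the halves be?**
- May 2016 to December 2018 is 32 months. May 2016 to the end of Q4 2017 is 20 months. At 48 per month, 1,076 / 48 = 22.4 months. These three do not agree.
- A switch at the calendar midpoint of the text (month 16) at 48 per month falls after 16 x 48 = 768 people: 768 / 1,076 = 71%.
- A switch at the midpoint of Table 1 (month 10) falls after 480 people: 480 / 1,076 = 45%.
- A switch by count gives 50%.

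**Effect on the pooled ratio.** Assume no CTC effect and a staff rate ratio r (the person giving CTC first, relative to the colleague), in the same direction in both cities. The apparent CTC ratio is [f r + (1 - f)] / [f + (1 - f) r]. For r = 0.7 and f = 0.6 this is (0.42 + 0.40) / (0.60 + 0.28) = 0.82 / 0.88 = 0.93.

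| Assumed r | 50/50 | 60/40 | 71/29 |
|---|---|---|---|
| 0.8 | 1.00 | 0.96 | 0.91 |
| 0.7 | 1.00 | 0.93 | 0.86 |
| 0.5 | 1.00 | 0.88 | 0.75 |

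At f = 0.446 and r = 0.7 the ratio is 0.866 / 0.834 = 1.04, so the error can go either way. The factor multiplies a true effect. With the halving expected in Section 13.2, a true 0.50 would read 0.50 x 0.93 = 0.47 at 60/40 or 0.50 x 0.86 = 0.43 at 71/29. It would read 0.54 or 0.58 if the staff difference ran the other way.

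**Cost of adjusting.** With interventionist and half as fixed terms, the variance inflation for arm is 1 / [1 - (2f - 1)^2]: 1.00 at 50/50, 1 / 0.96 = 1.04 at 60/40, and 1 / (1 - 0.428^2) = 1.22 at 71/29.

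**Could the switch test contamination?** Across both cities, four interventionist indicators plus half plus arm have rank 6. Adding arm-by-half leaves the rank at 6, because that contrast is already in the span of the interventionist terms. Power is also low. Suppose, purely as an illustration, a true ratio of 0.50 before the switch and 0.50 / 0.75 = 0.67 after it, with 200 per arm per half. Section 13.2's prior rate is 431 / 809 = 0.533 per year. Over six months the expected counts are 53.3 and 26.6 before the switch, and 40.0 and 26.6 after. The variance of the difference in log ratios is 1/53.3 + 1/26.6 + 1/40.0 + 1/26.6 = 0.119 (SE 0.345). The difference is ln(0.67 / 0.50) = 0.288, so z = 0.83 and power is about 13%. Over twelve months it is about 22%. Overdispersion would lower both.

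**The case against.** The best defence is that the switch already does the work. Each interventionist delivers both arms, half of accrual most naturally means half by count, and at 50/50 a constant staff difference vanishes from the pooled effect. This stands. A reader might infer from the within-half overlap that staff effects simply sit in the pooled CTC effect. The documents do not support that, because the design averages them out whenever the halves are near equal. The 71/29 case is also a deliberately unfavourable one: it combines the 32-month text with a monthly rate that would finish in 22.4 months.

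Other safeguards exist. Control participants' exposure to CTC content is asked about at six months (Section 3.19) and analysed with CACE methods (Section 13.1). Sessions are recorded and scored for fidelity, all of them in the first month and 10% afterwards (Section 3.11). Outcomes are collected by a research interviewer, a role named separately from the interventionist, which weakens the route through candour. These points make a large staff ratio less likely. None of them uses interventionist or half, so none corrects an unequal split.

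A reader might also treat the CTC effect before and after the switch as a direct test of leakage into control sessions. It is not one. The contrast is aliased with the difference between the two staff, its power is low, and all four interventionists train in and pilot CTC before accrual, so first-half control sessions are not a clean baseline. Finally, a reader might attach an inflated error rate to having only four interventionists. That needs an interventionist correlation that the documents do not give, and it concerns inference beyond these four people, which fixed terms would not change.

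**Conclusion.** The gap is real and limited. Arm and interventionist are identical within city and half, neither interventionist nor half is in the models, and the cancellation the design relies on is not secured: the halves are undefined, the accrual dates disagree and randomization is not stratified by city or half. The bias is nil at equal halves. For an assumed staff ratio of 0.7 it is about 7% at 60/40 and 14% at 71/29. It would be smaller if the staff differences ran in opposite directions in the two cities. The staff ratio and the split are both assumptions; the documents give neither. Main-effect terms remove only constant staff differences. Staff effects that change after the switch are aliased with arm and would remain. This does not undermine the trial, but the correction costs little.

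**What to change.** 1. Define the switch by participant count within each city, and reconcile the accrual dates in Section 3.14 with Table 1 and the monthly rate in Section 3.9.
2. Record the delivering interventionist and the accrual half for every participant.
3. Add interventionist (four levels, which also carries site) and accrual half as fixed terms in the H1 and H2 models.
4. State that inference is conditional on these four interventionists.
5. Optionally, show CTC effects by half as description, from a model without interventionist terms. Note beside them that arm-by-half is aliased with interventionist, has low power and does not test contamination.

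Cost: three interventionist contrasts plus one for half, so four covariates per modelled process. With treatment acting on the binary and count slopes, that is 8 parameters, or 16 if the intercepts are adjusted too, in about 800 people. The variance of the arm effect rises by a factor of 1.00 at equal halves and about 1.2 at 71/29. The variables should be available from the delivery schedule.
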